# **Renal Toxicity**

Immune-mediated nephritis or renal dysfunction occurred with nivolumab treatment. Patients should be monitored for elevated serum creatinine prior to and periodically during treatment and clinically monitored for symptoms of decreased volume of urination, hematuria, peripheral edema, loss of appetite.

[figure not shown]
In one trial, there was increased incidence of elevated creatinine in the nivolumab-treated group as compared to chemotherapy (13% v 9%). Grade 2 or 3 immune-mediated nephritis or renal dysfunction occurred in 0.7% (2/268) of patients. In another trial, the incidence of elevated creatinine was 22%, with Grade 2 immune-mediated renal dysfunction occurring in 0.9% (1/117) patients.

Renal toxicity should be managed according to the guidelines in Table below.

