Study IMP parameters definitions for dose level 1 are defined in the following table to derive relative dose intensity.

|                            | Pexa-Vec                                | Nivolumab                      |
|----------------------------|---|--------------------------------|
| Dose schedule per protocol | 109 pfu at D1, D15 and D29              | 240 mg every 2 weeks           |
| Actual Dose                | Actual dose expressed in pfu is defined | Actual dose expressed in mg is |
| * 9                        | as                                      | defined as Total dose (mg); as |

|  | (Total volume injected / Total volume prepared) x Dose Pexa-Vec (pfu); as reported in eCRF page "Pexa-Vec IT injection"                | reported in eCRF page "Nivolumab Administration"  |
|--|--|---|
| Actual Cumulative Dose                     | Actual Cumulative Dose expressed in pfu is defined as the sum of the actual doses  | Actual Cumulative Dose expressed in mg is defined as the sum of the actual doses  |
| Actual Dose Intensity (intensity per week) | Actual Dose Intensity expressed in pfu/wk is defined as Actual Cumulative Dose / [(Last administration - first administration + 14)/7] | Actual Dose Intensity expressed in mg/wk is defined as Actual Cumulative Dose / [(Last administration - first administration + 14)/7] |
| Planned Dose Intensity                     | 5 x 10  pfu/week   | 120 mg/week   |

All laboratory parameters will be expressed in the International System (SI) of units and the intensity grade using CTCAE version 4.03. A grade of 0 will be assigned when the value is within normal limits. In the case a local laboratory normal range overlaps into the higher (i.e., non-zero) CTC grade, the laboratory value will still be taken as within normal limits and assigned a CTC grade of 0. When normal limits are missing and needed for intensity grade determination, the grade will be set at missing. If normal limits are missing but not needed, grade intensity will be calculated as usual with CTCAE ranges.

Laboratory values recorded as "value < x" or "value > x" will be handled as equal to:

- x 0.001 if value recorded as "value < x"
- x + 0.001 if value recorded as "value > x"

for the calculation of descriptive parameters and for the value derived in SI units. Other methods could be investigated for specific parameters. In individual listings they will be presented as "< x" or "> x".

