## 8.8.2 Laboratory abnormalities

Listings of laboratory data will be provided by visit and displaying the Standard International (SI) units converted laboratory parameters with at least value, change from baseline, reference range, high/low, grade (if applicable) and clinical significance.

Laboratory data will be summarized at baseline by presenting descriptive statistics for all hematology and biochemistry parameters. All values will be displayed in SI units. A dedicated listing will be done for AFP results (reported in ng/mL).

Laboratory parameters (hematology and biochemistry) will be graded using the NCI-CTCAE version 4.03, dated June 14, 2010. A shift table of baseline CTCAE grade versus worst CTCAE grade during study will be presented for hematology and biochemistry parameters by Cohort (Cohort#1, Cohort#-1 and overall). For parameters with two directions abnormalities (decrease/increase), two shift tables will be presented. The list of laboratory parameters and their abnormalities graded according to CTCAE are presented in section 11.

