| Creatinine    | umol/L     | Investigations                     | Creatinine increased | >ULN - 1.5 x ULN;
>1 - 1.5 x baseline   | >1.5 - 3.0 x ULN; | >3.0 - 6.0 x ULN;
>3.0 baseline | >6.0 × ULN   |
| Glucose       | mmol/L     | Metabolism and nutrition disorders | Hypoglycemia         | <lln -="" 3.0="" l<="" mmol="" td=""><3.0 - 2.2 mmol/L	<2.2 - 1.7 mmoVL	<1.7 mmol/L	</lln>  | <3.0 - 2.2 mmol/L | <2.2 - 1.7 mmoVL                   | <1.7 mmol/L  |

Page 50/51

| Glucose                       | mmol/L     | Metabolism and nutrition disorders | Hyperglycemia                              | >ULN - 8.9 mmol/L | >8.9 - 13.9 mmol/L | >13.9 - 27.8 mmoVL | >27.8 mmol/L |
|-------------------------------|------------|------------------------------------|--|-------------------|--------------------|--------------------|--------------|
| Bilirubin                     | J/Jomd/L   | Investigations                     | Blood bilirubin increased                  | >ULN - 1.5 x ULN  | >1.5 - 3.0 x ULN   | >3.0 - 10.0 × ULN  | >10.0 × ULN  |
| Alanine
Aminotransferase   | U/L        | Investigations                     | Alanine aminotransferase increased         | >ULN - 3.0 x ULN  | >3.0 - 5.0 x ULN   | >5.0 - 20.0 × ULN  | >20.0 × ULN  |
| Aspartate
Aminotransferase | U/L        | Investigations                     | Aspartate
aminotransferase
increased | >ULN - 3.0 x ULN  | >3.0 - 5.0 x ULN   | >5.0 - 20.0 x ULN  | >20.0 × ULN  |
| Alkaline
Phosphatase       | U/L        | Investigations                     | Alkaline phosphatase increased             | >ULN - 2.5 x ULN  | >2.5 - 5.0 x ULN   | >5.0 - 20.0 × ULN  | >20.0 × ULN  |
|                               |            |                                    |  |                   |                    |                    |              |
| Lab Test Name                 | SI
Unit | CTCAE v4.03
SOC                 | CTCAE v4.03 Term                           | Grade 1           | Grade 2            | Grade 3            | Grade 4      |
|                               |            |                                    |  |                   |                    |                    |              |

|                          |            | •                                  |                                       |  |                    |                    |             |

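### The Grade 0 rule in SAP 7.7.2 switches off the baseline-relative creatinine criteria of SAP section 11 for results within normal limits, so a doubling from a low baseline can be tabulated as Grade 0 (minor)

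*SAP*

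**What the plan says.** Three parts of the SAP bear on how a creatinine result is graded.

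- **SAP 7.7.2, Derived variables.** The scope is general: "All laboratory parameters will be expressed in the International System (SI) of units and the intensity grade using CTCAE version 4.03". The rule follows: "A grade of 0 will be assigned when the value is within normal limits". Where a local normal range reaches into a non-zero CTC grade band, "the laboratory value will still be taken as within normal limits and assigned a CTC grade of 0". No parameter is exempted.
- **SAP section 11, Appendix 1.** The creatinine row has criteria relative to ULN and criteria relative to the patient's baseline. The legible baseline criteria are ">1 - 1.5 x baseline" at Grade 1 and ">3.0 baseline" at Grade 3. The Grade 2 cell shows a ULN criterion and then stops at a semicolon, so any baseline part cannot be read in this copy. In the readable appendix, no other parameter is graded against baseline.
- **SAP 8.8.2, Laboratory abnormalities.** Section 11 supplies the grading, and the output is specified thus: "A shift table of baseline CTCAE grade versus worst CTCAE grade during study will be presented for hematology and biochemistry parameters by Cohort". Listings give each result with its change from baseline, reference range, grade and clinical significance.

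SAP 7.7.2 also provides for calculated creatinine clearance in a table and a listing, without naming time points. The change history in SAP section 9 records that laboratory summaries over time were dropped in version 2.

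**The concern.** The two sections give different answers for the same in-range creatinine result. Section 11 treats a large rise over the patient's own baseline as a toxicity grade even if the value has not crossed ULN; 7.7.2 returns Grade 0 because it has not. Followed as written, 7.7.2 prevails, and part of the grading table that the SAP itself prints has no effect below ULN.

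At stake is whether the derived-grade shift table can show a marked loss of renal function in a patient who starts with a low creatinine. Creatinine matters in this trial. Safety is the Phase I primary objective, and Protocol Appendix 3 (Renal Toxicity) asks for creatinine monitoring because of immune-mediated nephritis, citing elevated creatinine in 13% and 22% of nivolumab patients in two trials. With six patients in a Phase I cohort, one patient is 1/6 = 17% of a shift table.

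**Working it through.** The plan states no figure on this point to reproduce. The check applies both rules to the same values.

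**Inputs.** Grade criteria: SAP section 11. Grade 0 rule and clearance formula: SAP 7.7.2. The documents give no creatinine normal limits, so these are assumptions: ranges of 40–80, 45–90, 50–110 and 60–110 µmol/L.

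**Main example (assumed ULN 110, LLN no higher than 50).** Creatinine rises from 50 to 105 µmol/L.

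- Fold rise: 105/50 = 2.1. This is past the Grade 1 baseline band and short of Grade 3. It is Grade 2 if the cut-off Grade 2 cell has a baseline part covering 1.5 to 3.0 times baseline. If it has none, it is Grade 1 when that grade is read as any lesser rise above baseline.
- Grade under 7.7.2: 0, because 105 ≤ 110.
- Clearance by the SAP formula for men, 1.23 × weight × (140 − age)/creatinine, at 70 kg and age 65: 1.23 × 70 × 75/50 = 129 mL/min before, and 1.23 × 70 × 75/105 = 61.5 mL/min after.
- Shift table entry: Grade 0 to Grade 0.

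**How low the baseline must be.** An f-fold rise stays at or below ULN only if baseline ≤ ULN/f.

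| Assumed ULN (µmol/L) | Highest baseline, 2-fold | Highest baseline, 3-fold |
|---|---|---|
| 80 | 80/2 = 40 | 80/3 = 26.7 |
| 90 | 90/2 = 45 | 90/3 = 30 |
| 110 | 110/2 = 55 | 110/3 = 36.7 |

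For baseline and follow-up both to be in range, ULN/LLN must be at least f. The assumed ranges give 80/40 = 2.0, 90/45 = 2.0, 110/50 = 2.2 and 110/60 = 1.83. A doubling wholly within range is therefore possible only from the low edge of the first three ranges and impossible in the fourth. A rise near three-fold needs a baseline below LLN in all four.

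**Edge case using legible text only.** With ULN 110, a rise from 35 to 108 µmol/L is 108/35 = 3.09 times baseline: Grade 3 in section 11, Grade 0 under 7.7.2. The rule also creates a step. From a baseline of 35, a value of 110 (3.14 times baseline) is Grade 0, and a value of 111 (3.17 times) is Grade 3.

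**Above ULN the baseline criteria still work.** With ULN 90, a rise from 40 to 130 is 130/40 = 3.25 times baseline and 130/90 = 1.44 times ULN. It is Grade 3 by baseline and Grade 1 by ULN, and 7.7.2 does not interfere.

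**What the Grade 0 rule prevents.** Without it, a rise from 50 to 60 µmol/L (1.2 times baseline) would be Grade 1.

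**The case against.** The strongest reply is that this is a stated convention and leaves no ambiguity. SAP 7.7.2 foresees normal ranges that overlap grade bands and says the normal range wins. The convention also has a sound purpose: it keeps trivial in-range fluctuation out of the tables. Both points stand. They settle which grade a programmer would produce, but they do not explain why section 11 prints baseline criteria that cannot act below ULN.

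Three stronger readings are tempting, and the documents do not support them.

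- **That the trial's safety profile understates renal toxicity.** Adverse events, immune-related events and dose-limiting toxicities come from investigator reporting on the eCRF and from their own definitions (SAP 8.8.1), and do not use the derived laboratory grade. Protocol 10.1 counts an abnormal laboratory finding as an adverse event. Protocol Appendix 3 gives immune-mediated nephritis or renal dysfunction in 2/268 and 1/117 patients. In the maximum of 47 patients that is 47 × 2/268 = 0.35 to 47 × 1/117 = 0.40 expected cases.
- **That two- to three-fold rises are routinely hidden.** The grade lost in that band depends on the Grade 2 cell, which cannot be read, and the upper end needs an unusually low baseline.
- **That the shift table is the only post-baseline creatinine summary.** Calculated clearance is also to be tabulated, its time points are not stated, and the list of tables is not readable here. Neither that claim nor its opposite can be established.

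**Conclusion.** The point holds in a narrow form. For a creatinine result within normal limits, SAP 7.7.2 disables the section 11 baseline criteria, and the grade that results departs from the SAP's own table. What is affected is the derived-grade shift table and the grade column of the laboratory listings. The realistic case is a patient with a low baseline whose creatinine about doubles: a baseline of at most 40–55 µmol/L for assumed ULNs of 80–110. A three-fold in-range rise, from a baseline of at most about 27–37 µmol/L, is an edge case.

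Severity is minor. Nothing here reaches the response-rate decision rule, the dose-limiting toxicity assessment or the adverse event tables, and the listings still show the value, its change and the calculated clearance. The size rests on assumed normal limits, and the number of patients affected cannot be estimated from the documents. The conflict itself rests only on the legible Grade 1 and Grade 3 cells and on the wording of 7.7.2.

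**What to change.** Add one exception to SAP 7.7.2: when a post-baseline creatinine exceeds 1.5 times the patient's baseline (as defined in SAP 7.7.1), the Grade 0 rule does not apply, and the grade is the worse of the ULN-based and baseline-based grades in section 11. Within normal limits, leave the Grade 1 baseline band suppressed, so that a rise such as 50 to 60 µmol/L stays Grade 0. Keep the Grade 0 rule unchanged for all other parameters.

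Before programming, check the Grade 2 creatinine cell in the source SAP. If it has no baseline part, complete the row; otherwise rises between 1.5 and 3.0 times baseline have no defined grade under the exception.

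The cost is one sentence, one programming exception and a few more graded creatinine elevations in the shift table. The 1.5-fold threshold is a judgement, chosen because it is the top of the printed Grade 1 band. If the sponsor prefers to keep the Grade 0 rule for creatinine, the SAP should say so explicitly and add a short table of maximum creatinine fold change from baseline.

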## 8 STATISTICAL METHODS

## 8.1 General principles

Statistical summaries will be produced using SAS® software version 9.4. The tables, listings and graphics will be prepared in landscape format.

Continuous variables will be described using: number of observations (N), arithmetic mean (Mean), standard deviation (sd), minimum (MIN), median (Median), the interquartile range (Q1-Q3) and maximum (MAX). One additional decimal point for mean, median, Q1 and Q3, and 2 additional decimal points for sd will be used. Data with more than 3 decimal places (if any), may not follow this rule: so 3 decimal places will be used.

Categorical variables will be presented using the number of observations (N) and percentages (%). Proportions will be displayed with one decimal and estimated with their exact (Clopper-Pearson) 95% CIs when appropriate.

All statistical testing will be two-sided at the 0.05 level without adjustments for multiplicity testing, unless specified otherwise. P-values will be presented to 3 decimal places. Any p-value less than 0.001 will be presented as <0.001, even if it would normally round up to 0.001.

## 8.2 Patient enrollment and disposition

## 8.2.1 Screening status

The number of patients screened (who gave informed consent) will be displayed for each part of the study (Phase I/Phase IIa) by cohort (Cohort #1, Cohort #-1 and overall). All patients who failed to meet eligibility criteria after ICF signature will be considered as screening failure and reported in the study report. The number of these patients and the primary reason for non-inclusion will be also displayed. Percentages will be calculated over the number of patients screened.

A listing will be performed to present all screen failures with the reason(s) of non-inclusion.

## 8.2.2 Population

A disposition table will display, for Phase I part and by cohort (Cohort #1, Cohort #-1 and overall), the number and percentage of patients (percentages based on enrolled patients) with:

- Patients enrolled
- Patients included in the SAF population
- Patients included in DLT population

A listing will be displayed with the reason from exclusion from DLT population.

A disposition table will display for Phase IIa part and by cohort (Cohort #1, Cohort #-1 and overall) the number and percentage of patients (percentages based on enrolled patients) with:

- Patients enrolled
- Patients included in ITT population
- Patients included in the PP population
- Patients from Phase I included in Phase II PP population (no percentage)
- Total number of patients included in PP population (Phase I and Phase IIa, no percentage)

The number and percentage of patients who were not included in the PP population will be presented by cohort (Cohort #1, Cohort #-1 and overall) for Phase IIa with the main reason for non-inclusion. The main reason for non-inclusion in the PP will be listed.

The number and percentage of enrolled patients (ITT population) will be also presented by country and site.

## 8.2.3 Status at the end of study

The status of patients at the end of study (completed / not completed) will be presented for each part of the study (Phase I/Phase IIa) by cohort (Cohort #1, Cohort #-1 and overall). For a patient, the study is considered as 'Completed' if the reason for study treatment withdrawal ("End of treatment" form of eCRF) is ticked "Progressive Disease" or "Maximum treatment duration (12 months)". This analysis will be conducted in the safety population.

The number and percentage of patients having withdrawn the study will be summarized for each part of the study (Phase I/Phase IIa) by cohort (Cohort #1, Cohort #-1 and overall) with the primary reason of withdrawal. The percent will be based on the safety population.

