## **DEFINITIONS**

Screened patient	A patient identified during the screening process achieved by the Investigator as a candidate to the study and invited to sign the informed consent form.	
Consented patient	A patient who has signed the informed consent form.	
Not included patient	A consented patient who did not receive the Investigational Medicinal Product.	
Eligible patient	A consented patient fulfilling all inclusion and exclusion criteria	
Included patient	A patient having received the first Investigational Medicinal Product administration.	
Treated patient	A patient having received at least the first Investigational Medicinal Product administration as planned by the protocol.	
Ongoing patient	A patient included, presently treated according to the protocol requirements.	
Withdrawn patient (= drop-out patient)	An included patient who leaves the study between the inclusion date and the end of study visit whatever the reason.	
Completed patient	A patient who has completed all procedures up to the "end of study visit" as planned by the study protocol.	
= =	Phase I section: a patient having completed the Dose-Limiting Toxicity period (scheduled on Day 29) and having received all 3 Pexa-Vec intra-tumoral treatments and 2 nivolumab infusions.	
Evaluable patient	Phase IIa section: a patient having received at least 2 administrations of Pexa-Vec and 2 administrations of nivolumab and undertaken at least one post-baseline radiological assessment or exhibited any evidence of disease progression other than radiological.	
Lost to follow-up patient	An included patient for whom no further news is obtained by the Investigator before the "end of study visit" has been performed. The date of lost to follow-up is the date the Investigator received the last news from the patient i.e. during a visit or a telephone contact or any written means.	
End of study	The date of the last visit of the last patient undergoing the study.	
Protocol deviation	All non-adherences to following protocol requirements: stud	

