#### 6.6 Premature withdrawal of patients

#### 6.6.1 Circumstances

The patient's participation in the protocol may terminate under any of the following circumstances:

- Patient's request at any time for any reason,
- Physician's determination that patient's further participation in the protocol is not in the patient's best interest,
- Need to treat the patient with a prohibited medication,
- Transgene's decision (for example in case of new fact or toxicity issue regarding the IMP),
- Health Authorities' decision.
- Unacceptable toxicity associated with any IMP,

- Progressive disease after consideration of possible treatment continuation.

For any discontinuation, the Investigator will obtain all the required details and document the date of and the reason for the discontinuation in the eCRF. In any case of treatment cessation not related to disease progression the patient will be followed per protocol until documentation of progressive disease (PFS visits).

If the reason for stopping the treatment is an AE, the specific event will be recorded in the eCRF. The Investigator will make thorough efforts to document the outcome.

As far as possible, no patient should leave the study without having undergone the end of study visit.

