## Follow-up

AE/SAE must be followed until resolution or the last visit planned by the protocol, i.e. end of study visit, occurring 28 days after last study treatment administration or after disease progression, whichever is the latest.

However, the AE listed below must be followed until they are resolved or stable or returned to Baseline status, which may occur after the last visit planned by the protocol:

- AE evaluated as related to the IMP,
- SAEs.
- Any other significant AE as recommended by Transgene i.e. formation of skin pustules.

In addition to the collection in the eCRF, follow-up information about the development of skin pustules will be reported to Transgene in an expedited manner within 24 hours of knowledge by the Investigator as indicated in the eCRF.

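### SAP 8.2.3 sets study completion from the reason treatment stopped, while the protocol sets it by the end of study visit, so the status table can misclassify patients in both directions

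*SAP*

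**What the plan says.** SAP 8.2.3 (Status at the end of study) reports completed or not completed by study part and cohort. Its rule is that "the study is considered as 'Completed' if the reason for study treatment withdrawal" is ticked as progressive disease or as "Maximum treatment duration (12 months". It adds: "This analysis will be conducted in the safety population". A second paragraph of the same section tabulates patients who withdrew from the study, with the primary reason.

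The protocol's Definitions table uses a different anchor:

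- A completed patient is "A patient who has completed all procedures up to the" end of study visit.
- A withdrawn patient is "An included patient who leaves the study between the inclusion date and the end of study visit whatever the reason".
- A patient lost to follow-up is "An included patient for whom no further news is obtained by the Investigator before the" end of study visit has taken place.

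Protocol 10.4 (Follow-up) places the last planned visit as follows: "i.e. end of study visit, occurring 28 days after last study treatment administration or after disease progression, whichever is the latest". Protocol 6.6.1 states: "In any case of treatment cessation not related to disease progression the patient will be followed per protocol until documentation of progressive disease". Sections 8.11 and 8.12 agree. Patients who stop without progression remain in active participation on PFS visits, and their end of study visit comes only once they have progressed. If progression came first, the end of study visit is merged with the safety visit due at least 28 days after the last dose.

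**The concern.** The two documents measure different things under one label. The SAP row records why treatment stopped. The protocol term records whether the patient was seen through to the end of study visit. In this trial the two events can be well apart, because stopping treatment without progression starts a further period of PFS follow-up.

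A reader of the study report who takes the completion rate in the protocol's sense would be misinformed about how fully patients were followed. The two paragraphs of 8.2.3 may also fail to fit together. If withdrawals are counted by the protocol definition, one patient can be both completed and withdrawn.

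**Working it through.** No arithmetic applies, so the check takes each plausible patient path through both rules. The inputs are the 8.2.3 rule, the stop reasons listed in SAP 8.6.3 (which include clinical progression and unacceptable adverse event as categories separate from progressive disease), the protocol Definitions, and the visit rules in protocol 6.6.1, 8.11, 8.12 and 10.4.

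| Path | SAP 8.2.3 | Protocol |
|---|---|---|
| Stops for progression, attends the end of study visit | Completed | Completed |
| Stops for an adverse event before progression, has PFS visits to progression, attends the end of study visit | Not completed | Completed |
| Treated beyond progression (allowed by protocol 6.1.2.2), later stops with adverse event as the ticked reason, attends the merged visit | Not completed | Completed |
| Stops for clinical progression, is followed to documented progression, attends the end of study visit | Not completed | Completed |
| Stops for progression, then dies, withdraws or is lost before the visit | Completed | Not completed |
| Stops at a 12-month maximum without progression, leaves during PFS follow-up | Completed | Withdrawn |

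Only the first path gets the same status. The next three are completers that the SAP rule misses, and the last two are non-completers that it counts. The error therefore runs both ways, and the paths can offset each other.

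**Overlap within 8.2.3.** The patients in the last two rows leave before the end of study visit. Under the protocol definition they belong in the withdrawn summary in the second paragraph of 8.2.3, while the first paragraph calls them completed.

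**The 12-month category.** SAP 5.2 and protocol 6.1.2.2 give nivolumab with no time cap. Protocol 6.1.3 mentions 12 months in a statement on expected study duration, which it ties to the scan schedule. Its next paragraph continues scans every 12 weeks beyond 12 months. Protocol 8.11 keeps unprogressed patients in PFS follow-up past that point. In the supplied text, then, reaching 12 months of treatment does not end a patient's participation.

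**Where the flag is used.** The safety, DLT, per protocol and intent-to-treat sets in SAP 6.1 do not refer to it. Neither do the stopping rules in 7.3.3 or the efficacy definitions in 8.7.

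**The case against.** The strongest reply has four parts.

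**The version.** SAP section 1 says the plan was built on the protocol of 22 December 2017 and eCRF version 6.0. SAP version 3 (December 2018) predates the supplied protocol of 20 March 2019. This stands, and it applies to the whole conflict, not only to the 12-month item. A reader might infer that the SAP contradicted the protocol it was implementing, or that the 12-month tick box is itself a mistake. The documents support neither inference, because the earlier protocol and the eCRF are not available.

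**Withdrawals are already reported.** The second paragraph of 8.2.3 gives them with the primary reason. This stands in part. Patients who stop for progression and then leave need not vanish from the report, so it would be wrong to say that the SAP hides them. It does not help patients wrongly labelled not completed, and it creates the possible overlap between the two rows.

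**The rule is stated openly, and 8.6.3 summarises stop reasons and the week of the end of study visit.** True, and this limits the harm. It does not make a rate labelled completed agree with the protocol's meaning of the word.

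**The protocol wording is itself strict.** Read literally, one missed procedure would make a patient a non-completer. That is fair, and it is a reason to base the revised rule on attendance at the visit rather than on a full procedural check.

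**Conclusion.** The point holds as a minor inconsistency that produces wrong counts in one descriptive table. Confidence is moderate, because the conflict can be shown only against the March 2019 protocol.

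The number of patients affected cannot be derived, since the documents give no frequencies for any of the paths. A reader might be tempted to size it by one patient in a Phase I cohort of six, 1/6 = 16.7 percentage points. That is only the grain of the table. It does not estimate the error, and even the sign of the net effect is unknown.

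Nor should a reader infer any effect on the response rate, the time-to-event endpoints, the analysis sets or the interim decision.

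**What to change.** Revise SAP 8.2.3 along these lines:

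- **Completed:** attended the protocol end of study visit after disease progression.
- **Withdrawn:** left the study before that visit, with the primary reason, and with deaths shown separately. This includes patients who leave prematurely but are given an early closing visit, as protocol 6.6.1 and 6.7 encourage.
- The two rows are mutually exclusive. Patients still on study at a cut-off belong in neither.
- Reaching a 12-month treatment maximum does not count as study completion.
- Reasons for stopping treatment stay in 8.6.3.

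The cost is a few lines of SAP text and reprogramming one table. The SAP already plans to summarise the week of the end of study visit, the stop reason and the withdrawal reason, and it derives PFS from the progression date. No new data collection should be needed, although the eCRF should be checked because it was not supplied.
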